1.4 Study Rationale and Risk Analysis (Risks to Benefits Ratio)

1.4.1 Study Rationale

We hope to further characterize and define the role of consumer-facing technology in the clinical environment by focusing on device accuracy when compared to standard clinical monitoring in patients undergoing an endoscopic procedure. We will generate and answer questions related to these devices that have not yet been explored in the gastroenterology literature. We will provide a timely and much-needed framework that addresses both practical and theoretical considerations around a technology that has become increasingly relevant to patients.

This study will specifically address whether consumer facing wearable devices can serve as patient monitoring devices in a comparable manner to the current gold standard in the procedural suite. In addition to accuracy, we will assess whether certain procedural maneuvers interfere with device data collection. This information will be relevant to patients, providers and healthcare institutions and can help inform policy regarding these devices.

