2.1 Primary Objective

Measure the accuracy of wearable technology for patient monitoring compared to currently used equipment in patients undergoing gastrointestinal endoscopic procedures with sedation

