3.1 General Design

We will perform a prospective, non-blinded, exploratory study to assess the accuracy and safety of smart technology in the endoscopy suite for patients undergoing gastrointestinal endoscopic procedures with sedation. We will also simultaneously perform an assessment of patient and provider preferences using narrative-driven, qualitative evaluation.

Patients will be identified by reviewing daily procedure listings on endoscopy units on Alfred 6, Gonda 2 and Gonda 9. Recruitment will occur over the phone the day prior to a procedure, or the pre-procedure areas on the day of the procedure. Patients who meet inclusion criteria and consent to participation in the study will be provided the smart devices. The devices will be secured to the wrist and torso by study personnel prior to administration of sedatives. The smart watch will be programmed to record respiratory rate, heart rate, and oximetry using native, first party device applications. These applications include *Blood Oxygen* (measures oxygen saturation), *ECG* (records single lead ECG), *Heart Rate* (heart rate), and *Health* (which logs respiratory rate while sleeping). The QardioCore ECG device will measure a single-lead ECG, heart rate, skin temperature, and respiratory rate.

The patient will undergo his or her scheduled procedure. Patients, proceduralists and anesthetists will not be blinded to their enrollment as the devices will be visible. On completion of the procedure, the devices will be removed by the study coordinator and data downloaded onto a central device for analysis. Procedural information will be extracted from the operative note, sedation record, and anesthesia encounter in EPIC. The day after the patient's procedure, a survey will be submitted to them electronically which will remain open until 14 days after

the procedure. Aen electronic reminder will be sent if uncompleted at 7 days, followed by a telephone reminder if not completed at 13 days. There will be no additional patient follow up after completion of the survey. At study completion, a survey will be sent to involved proceduralists and anesthetists.

3.2

Figure 1: Study Design

[figure not shown]

Table 1. Schedule of Events

	Baseline Screening & Enrollment Visit 1 Days -60 to 0	Accrual: Study Intervention Visit 2 Day 0	Patient Survey Visit 3 Day +1 to +14	Provider survey Days 0 to 180
Inclusion/ Exclusion	X	X (if not performed earlier)		
Device(s) Placement/ Recording		X		
Patient Survey			X	

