5.2 Statistical Methods

Descriptive Statistics

Baseline values for demographic, clinical, and outcome will be tabulated for the study subjects. Continuous variables will be expressed as mean and standard deviation. Categorical variables will be expressed as percentages.

We will measure the rate of concordance between device detection and documentation in anesthesia record (# of events recorded on wearable device / events noted on anesthesia record). Events to be recorded include tachycardia (HR > 100), bradycardia (HR < 60), desaturation (peripheral O₂ saturation < 88%), any arrhythmia, and tachypnea (RR > 18).

We will also calculate the difference in maximum and minimum heart rate, respiratory rate, and oxygen saturation recorded by the watch compared to the sedation record.

Handling of Missing Data

Subjects with missing or incomplete data will be noted but will not include in the final analysis. Available information regarding these patients will be reported separately to allow for evaluation of external validity

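### The accuracy objective rests on differences in maximum and minimum readings, with no common window, recording interval or time pairing, so each difference mixes accuracy with how the two sources record

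*Combined protocol and SAP*

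**What the plan says.** Section 2.1 gives the primary objective: "Measure the accuracy of wearable technology for patient monitoring compared to currently used equipment". Section 1.4.1 adds the question whether wearables "can serve as patient monitoring devices in a comparable manner to the current gold standard in the procedural suite".

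For continuous readings, section 5.2 plans one comparison with the reference: to "calculate the difference in maximum and minimum heart rate, respiratory rate, and oxygen saturation recorded by the watch compared to the sedation record". Its only general rule for summarising such quantities is "Continuous variables will be expressed as mean and standard deviation". The concordance ratio in the same section counts threshold events. It is a separate measure and not part of this point.

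On timing, section 3.1 says "The devices will be secured to the wrist and torso by study personnel prior to administration of sedatives" and "On completion of the procedure, the devices will be removed by the study coordinator and data downloaded onto a central device for analysis". On the reference side it says "Procedural information will be extracted from the operative note, sedation record, and anesthesia encounter in EPIC". Section 5.3 keeps only subjects who wore the device throughout the procedure. The documents do not state a recording interval for either source, the period that the sedation record covers, clock alignment, or any pairing of readings by time. Section 5.1 says that the study is descriptive and that no testing is planned.

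**The concern.** A maximum or minimum depends on more than the accuracy of the instrument. It also depends on how many readings were taken, how noisy they were and how long recording lasted. The plan does nothing to make these equal between a watch running its own applications and a charted clinical record.

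Two questions are being answered with one number. Whether a watch captures the peak and nadir that the record shows is a fair question for a monitor, and it fits section 1.4.1. Whether its readings are accurate is the primary objective, and it is a different question. If the max/min difference is reported as accuracy, an accurate watch can appear to read high or low because of its recording schedule, and a real offset can disappear from one of the two extremes. No test or decision rule depends on the figure, so what is at stake is a misread accuracy estimate.

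**Working it through.** The plan states no figure to reproduce. The check is whether recording frequency, noise or duration alone moves the planned quantity when the watch is accurate, and what can be recovered from the two reported differences.

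**Inputs, all assumed because the documents give none.** Heart rate is a first-order autoregressive series on a 5-second grid for 30 minutes (361 points). Within-patient SD is 8 bpm and correlation time runs from 1 to 30 minutes. The record is charted every 5 minutes (7 values). There are 20,000 simulated patients per setting. The quantities are max(watch) - max(record) and min(watch) - min(record).

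**Step 1: error-free watch, frequency only.** Ranges run over the correlation times.

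| Watch reads | Mean maximum difference (bpm) | Mean minimum difference (bpm) |
|---|---|---|
| at the record's times | 0 | 0 |
| every 5 s | +2.0 to +9.4 | -2.0 to -9.4 |
| every 15 min, in phase with charting | -1.3 to -4.0 | +1.3 to +4.0 |
| every 15 min, random phase | -3.1 to -6.3 | about +3.1 to +6.2 |

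With charting every minute, the maximum differs by about +1 to +4 bpm (5-second watch). For a 15-minute watch it differs by about -3 to -9 bpm in phase and -4 to -11 bpm in random phase. Scaling the first and third rows of heart-rate differences by 3/8, for an assumed respiratory-rate SD of 3/min, gives +0.8 to +3.5 (5 s) and -0.5 to -1.5 (15 min, in phase).

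**Step 2: noise only, and duration only.** Unbiased noise of SD 4 bpm at identical times gives a maximum difference of +1.3 to +2.2 and a minimum difference of -1.3 to -2.2. If the watch records for 15 minutes longer at the same 5-minute spacing, the maximum differs by +1.5 to +1.7. This returns to 0 when both are cut to the shared period.

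**Step 3: a watch that truly reads 5 bpm high.** Write b for the offset and f for the frequency effect of step 1. The maximum difference is b + f, and in a symmetric model the minimum difference is b - f.
- Every 5 s: maximum 5 + 2.0 = +7.0 to 5 + 9.4 = +14.4. Minimum 5 - 9.4 = -4.4 to 5 - 2.0 = +3.0.
- Every 15 min, in phase: maximum 5 - 4.0 = +1.0 to 5 - 1.3 = +3.7. Minimum about +6.4 to +9.1.
- Every 15 min, random phase: maximum 5 - 6.3 = -1.3 to 5 - 3.1 = +1.9, so the offset nearly vanishes from the maximum.

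**Step 4: what the two extremes recover together.** The average, [(b + f) + (b - f)]/2 = b, returns the offset: (14.4 - 4.4)/2 = 5.0 and (1.0 + 9.1)/2 = 5.05. So offset and frequency separate under symmetry. The half-difference f does not separate noise from density. At a 30-minute correlation time, an error-free 5-second watch gives about +2.0 and -2.0, and a watch with 4 bpm noise read at the charting times gives about +2.2 and -2.2.

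**Step 5: a capped measure.** Suppose saturation is flat apart from one 60-second dip of depth D, and each source holds spot values. The chance that a source holds the dip is dip length divided by interval, capped at 1: 100% at 5 s, 60/300 = 20% at 5 min, 60/900 = 7% at 15 min. For an error-free 5-second watch against 5-minute charting, the mean minimum difference is -(1.00 - 0.20)D = -0.8D and the maximum difference is 0. Their average is -0.4D, an apparent offset where none exists.

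**Step 6: time pairing.** Pairing each record value with the nearest watch value gave a mean difference within 0.1 bpm of zero for the error-free watch, and +4.9 to +5.0 bpm for the watch reading 5 bpm high.

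**The case against.** The strongest reply is that the plan reports both extremes. An offset moves them the same way and recording frequency moves them in opposite directions, so a careful reader can separate the two. Step 4 bears this out. A reader might infer that the planned outputs cannot tell an inaccurate sensor from a sparse or dense one at all. The documents do not support that, because section 5.2 asks for the maximum and the minimum. What remains confounded is a noisy sensor with a dense one, and any skewed or capped measure.

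A second reply is that the plan never says the readings will be unmatched. That is right: the text is silent, and the defect is that nothing assures matching. Section 5.3 also ensures that the device was worn throughout the procedure, so the window problem mainly concerns the edges, such as readings before sedation.

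Third, the sizes are assumed. That stands in full. The +9.4 bpm figure needs a 5-second watch, 5-minute charting and a 1-minute correlation time together.

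Fourth, the study is exploratory and extremes matter to a monitor. Both are true, but describing accuracy is still the stated objective.

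Fifth, pairing has its own weakness: the time gap between paired readings inflates the limits of agreement. That is also true, and it shapes the fix.

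**Conclusion.** The point holds in a limited form. The mechanism is well established: unless the sources share reading times and window, the max/min difference is not a measure of accuracy alone, and section 5.2 offers no other comparison of continuous readings. A constant offset can be recovered from the two extremes if readings are roughly symmetric. Sensor noise cannot be separated from recording density, and for oxygen saturation the separation need not hold.

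The size in this study cannot be found from the documents. Under the assumed 30 minutes, SD of 8 bpm and 5-minute charting, an error-free watch shows a mean maximum difference from about +9 bpm (every 5 s) to about -6 bpm (every 15 min, random phase), and 0 at identical times. A reader might infer that a bias of that order is present here, or that a test would go wrong. Neither follows, since no intervals are given and no test is planned. The plan should be changed because the remedy is cheap and serves the primary objective directly.

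**What to change.** Amend section 5.2 as follows.

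1. Restrict both sources to the period that both recorded.
2. First confirm that serial, time-stamped sedation-record values can be extracted; section 3.1 mentions only procedural information. Where they can, make the accuracy analysis the difference between each record value and the nearest watch value within a prespecified window. Report the mean difference and 95% limits of agreement, allowing for repeated readings per patient, with the number of pairs, the patients contributing and the time gap.
3. Read limits from a wide window as upper bounds. Where pairs are few, as may happen for respiratory rate, which section 3.1 says the watch logs during sleep, give counts and a descriptive summary only.
4. Keep maximum and minimum over the common window, with the number of readings per source, and label them as capture of extremes, not accuracy.

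None of this needs a hypothesis test, so it is consistent with section 5.1. Whether the chest device should enter the comparison is a separate matter.

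The cost is SAP wording, data extraction and clock alignment, with no extra patients. The main downside is few pairs for sparse parameters. With 5-minute charting over 30 minutes and random watch phase, a window of ±30 s gives 7 pairs per patient for a 5-second watch, 1.3 for a 5-minute watch and 0.44 for a 15-minute watch (0.44 x 500 = 220 in all). In the last two cases about 78% of patients have no pair. A window of ±150 s gives 6.0 and 2.0 pairs for those two and leaves no patient without one. However, the time gap alone then widens an error-free watch's limits (1.96 x SD of the paired difference) from about ±2.0 to ±10.5 bpm up to about ±4.5 to ±17.7 bpm, depending on correlation time.

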3.3.2 Clinical Procedure/Accrual (Visit 2)

The devices will be secured to the wrist and torso by study staff prior to administration of sedatives. The devices will be programmed to record respiratory rate, heart rate, oximetry, skin temperature as well as single-lead ECG. The patient will undergo his or her scheduled procedure. On completion of the procedure, the devices will be removed by the study staff will download data onto a central device for analysis.

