5.3 Subject Population(s) for Analysis

All subjects who wore the device for the duration of procedure will be included in the analysis.

6 Safety and Adverse Events

Patients will be undergoing endoscopic procedures that are clinically indicated with inherent risk of the procedure itself. There will be minimal additional risk with placement of a smart device in the pre-operative area. Wearable technologies (eg. smartphones, smart watches) are already permitted in the endoscopy suite, so this protocol would not significantly alter standard of care. Therefore, this study will not track any adverse events.

Definitions

Adverse Effect (Event)

Any untoward medical occurrence in a subject involved in clinical study of an investigational device; regardless of the causal relationship of the problem with the device or, if applicable, other study related treatment(s).

Life-threatening adverse effect: Any adverse effect that places the subject, in the view of either the investigator or the sponsor, at immediate risk of death from the effect **as it occurred**. It does not include a reaction that, had it occurred in a more severe form, might have caused death.

Serious adverse effect: An adverse effect is considered “serious” if, in the view of either the investigator or the sponsor, it results in any of the following outcomes:

- death
- a life-threatening AE
- inpatient hospitalization or prolongation of existing hospitalization
- a persistent or significant disability/incapacity
- a congenital anomaly/birth defect.

Unanticipated adverse effect: Any adverse effect, the nature, specificity, severity, or frequency of which is not consistent with the risk information in the clinical study protocol or elsewhere in the current IDE application.

All inclusion and exclusion criteria are set out and there will be no protocol deviation.

7 Data Handling and Record Keeping

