7.1 Confidentiality

Information about study subjects will be kept confidential and managed according to the requirements of the Health Insurance Portability and Accountability Act of 1996 (HIPAA). Those regulations require a signed subject authorization informing the subject of the following:

- What protected health information (PHI) will be collected from subjects in this study?
- Who will have access to that information and why?
- Who will use or disclose that information?
- The rights of a research subject to revoke their authorization for use of their PHI.

In the event that a subject revokes authorization to collect or use PHI, the investigator, by regulation, retains the ability to use all information collected prior to the revocation of subject authorization. For subjects that have revoked authorization to collect or use PHI, attempts should be made to obtain permission to collect at least vital status (long term survival status that the subject is alive) at the end of their scheduled study period.

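### Section 5.2 drops the whole subject for any missing or incomplete data, although the comparisons are made parameter by parameter on two devices

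*Combined protocol and SAP*

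**What the plan says.** Section 5.2, under the handling of missing data, says: "Subjects with missing or incomplete data will be noted but will not include in the final analysis". It then adds: "Available information regarding these patients will be reported separately to allow for evaluation of external validity". No section says whether completeness is judged by device, by parameter or by length of recording.

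The comparisons in 5.2 are made by parameter. One is a concordance ratio for five kinds of event: fast and slow heart rate, desaturation, arrhythmia and fast breathing. The other is "the difference in maximum and minimum heart rate, respiratory rate, and oxygen saturation recorded by the watch compared to the sedation record".

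The recording is wider than the comparisons. The Study Summary has two devices placed on each subject. Section 3.1 lists watch applications for saturation, ECG, heart rate and respiratory rate, the last in an application "which logs respiratory rate while sleeping". For the torso device it says: "The QardioCore ECG device will measure a single-lead ECG, heart rate, skin temperature, and respiratory rate". Section 3.3.2 repeats the combined list: "The devices will be programmed to record respiratory rate, heart rate, oximetry, skin temperature as well as single-lead ECG".

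Section 5.3 defines the analysis population: "All subjects who wore the device for the duration of procedure will be included in the analysis". Sections 4.4.1 and 4.4.2 count discretionary removal of the devices before the procedure ends as early withdrawal. They keep a record of such subjects for the withdrawal rate and make no further use of their data.

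**The concern.** Measuring accuracy is the primary objective (section 2.1). A rule that removes subjects, rather than missing values, has two effects on that estimate.

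First, it discards good data. A subject with sound heart rate and saturation readings but no watch respiratory rate leaves the final analysis. So, on a literal reading, does a subject lacking only skin temperature, for which 5.2 plans no comparison at all.

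Second, it removes the recordings that failed. Section 1.4.1 says the study will look at whether steps in the procedure disturb device recording. If they do so by causing gaps, the affected subjects are the ones taken out of the accuracy figure.

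Because the plan does not define incompleteness, two analysts could both follow it and report accuracy on different sets of subjects. A descriptive study without testing still needs a defined denominator.

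**Working it through.** The plan gives no figure to reproduce. Section 5.1 reports no power analysis, and no section states an expected rate of missing readings. The check therefore compares the text and then illustrates the possible loss.

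**Text.** Take a subject who wears both devices throughout but has no watch respiratory rate.

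- Section 5.3 includes this subject, because it asks only about wear.
- Section 5.2 excludes this subject if one absent parameter makes the data incomplete.
- If 5.2 is read as a filter applied after 5.3, the two can stand together. The filter still depends on an undefined term, and 5.3 still speaks of one device where two are worn.

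**Inputs.**

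- N = 500 planned subjects (section 4).
- k = number of signals that must be present. k = 3 for the watch parameters with a planned maximum and minimum comparison. k = 8 for every signal listed in 3.1 (four watch, four torso).
- p = share of subjects missing each signal. This is assumed at 2%, 5% and 10%, and is not from the documents.

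**Formulas.**

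- Analysis by parameter: N(1 − p) for each signal.
- Whole-subject exclusion, gaps fully shared: N(1 − p).
- Whole-subject exclusion, gaps independent: N(1 − p)^k.
- Whole-subject exclusion, gaps never overlapping: N(1 − kp).

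**At p = 5%.**

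- By parameter: 500 × 0.95 = 475.
- k = 3: 500 × (1 − 0.15) = 425 at the lower bound; 500 × 0.95³ = 428.7 if independent; 475 if fully shared.
- k = 8: 500 × (1 − 0.40) = 300 at the lower bound; 500 × 0.95⁸ = 331.7 if independent; 475 if fully shared.

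| Assumed p | By parameter | k = 3: range (independent) | k = 8: range (independent) |
|---|---|---|---|
| 2% | 490 | 470–490 (470.6) | 420–490 (425.4) |
| 5% | 475 | 425–475 (428.7) | 300–475 (331.7) |
| 10% | 450 | 350–450 (364.5) | 100–450 (215.2) |

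The top of each range equals the by-parameter figure: if the same subjects lack every signal, whole-subject exclusion costs nothing extra.

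**The case against.** The strongest reply is that the plan is open about what it does. It says that these subjects stand outside the final analysis, reports their available information separately and records withdrawals. Accuracy given a usable recording is a legitimate descriptive quantity, and the study is exploratory. This stands as far as visibility goes. It does not return valid readings to the parameters they belong to, and it does not define the rule.

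Several stronger readings are tempting, and the documents do not support them:

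- *Sections 5.2 and 5.3 contradict each other.* A population followed by a missing-data exclusion is an ordinary structure, and the sections are adjacent. This is a repair of wording.
- *Section 4.4.2 conflicts with 7.1.* Section 7.1 says that the investigator "retains the ability to use all information collected prior to the revocation of subject authorization". That is a regulatory permission attached to a different event. A study may choose a stricter rule.
- *The undefined term alone moves the analysed number from about 429 to about 332.* That needs independent gaps. Signals from one device can fail together through poor contact, removal or download, and with fully shared gaps the difference is zero.
- *The watch will lack respiratory rate under sedation.* No section says how the watch treats sedation, and the torso device also measures respiratory rate. The gap is a possibility only.

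The counts of three and eight are also reference points. Arrhythmia needs a further input beyond the three, and the Study Summary names the devices as examples, so eight is not a fixed protocol number.

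**Conclusion.** The point holds as a choice of analysis that should be fixed. As written, 5.2 discards valid readings because another signal is missing, and it takes subjects whose recording failed out of the primary accuracy estimate. This follows from the text alone and needs no assumed rate.

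The size does need assumptions. With 5% missing per signal, between 0 and 50 further subjects are lost for each parameter if three signals are required (475 − 425 = 50), and between 0 and 175 if eight are (475 − 300 = 175). Where the figure falls depends on how far the gaps overlap, which the documents do not say.

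A reader might infer that the rule will make the devices look more accurate than they are. The documents give no concordance and no failure rate for either group of subjects, so neither the direction nor the size of any bias can be derived.

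**What to change.** In 5.2, replace whole-subject exclusion with analysis of each device and parameter on its own available data. Where a recording is partial, take the events, maximum and minimum from the same time window of the sedation record, because all three depend on how long one observes. Report the capture rate by device and parameter, with the reason for each gap. Label the concordance figure as conditional on an available device reading. In 5.3, align the wording with 5.2 and name the device or devices meant.

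As a secondary matter, the sponsor may reconsider whether readings taken before a discretionary device removal (4.4.1 and 4.4.2) can be kept where consent allows. Section 7.1 does not require this.

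The cost is protocol and SAP wording, logging of gap reasons, and time alignment of device and record data for partial recordings, which no section now specifies. The reported result may be less favourable.
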